6.12 Pharmacokinetic Analyses

Pharmacokinetic concentration data will be summarized using descriptive statistics (n, mean, standard deviation, median, minimum and maximum) at each time point. Also CV%, geometric mean, geometric SD and geometric CV% will be presented.

Geometric mean is calculated as

$$\mu_g = \sqrt[n]{x_1 x_2 x_3 \dots x_n},$$

where n is the number of observations and x_i are the observed data. This can be expressed also in the following form

$$\mu_g = \exp\left(\frac{\sum_{i=1}^n \ln x_i}{n}\right),$$

which is easier for the practical calculation. This would simply be the exponent of the arithmetic mean from logarithmically transformed data.

Geometric standard deviation (SD)

Geometric SD is calculated as

$$\sigma_g = \exp\left(\sqrt{\frac{\sum_{i=1}^n (\ln x_i - \ln \mu_g)^2}{n}}\right).$$

This would simply be the exponent of the arithmetic standard deviation from logarithmically transformed data.

Geometric coefficient of variation (CV)

Geometric CV is calculated as

$$CV_g = \sqrt{e^{(\ln \sigma_g)^2} - 1},$$

where $\ln \sigma_g$ is the arithmetic standard deviation from logarithmically transformed data.

Geometric CV can be multiplied by 100 if CV displayed in percentage.

6.13 Pharmacodynamic Analyses

Controlled Quality Management Document		
	Sponsor:	Veru Inc.
	Protocol Number:	V3011902
STATISTICAL ANALYSIS PLAN. PHASE 2-3-4		

Not applicable.

6.14 Safety Analyses

The safety analyses will be presented by the treatment received for the Safety Analysis Set.

6.14.1 Adverse Events

A treatment emergent adverse event (TEAE) is defined as:

- Any AE that has an onset on or after the first dose of study drug.
- Any pre-existing AE that has worsened in severity on or after the first dose of study drug.

A treatment-related AE is defined as an AE with causality collected as 'POSSIBLY RELATED', 'PROBABLY RELATED' or 'RELATED' in the CRF.

The intent is to collect all data, in a rare cases data might be incomplete for AE relationship and/or standard toxicity grade. This is not anticipated to cause any issues in the analysis and in these cases values will be imputed using worst-case scenario for analysis as follows:

- If an AE has missing relationship it is assumed to be 'RELATED' to the study drug for analysis purposes.
- If an AE has missing standard toxicity grade it is assumed to be 'GRADE 3 (SEVERE)' for analysis purposes. This is not worst case but more meaningful to impute as severe compared to life-threatening or death.

AEs will be summarized according to the MedDRA (version 24.0) system organ class and preferred term.

The following tables will be presented for AEs:

- Overall incidence and the number of events in the following categories:
 - TEAEs
 - Treatment-Related TEAEs
 - Serious TEAEs
 - Treatment-Related Serious TEAEs
 - TEAEs leading to treatment modification (drug interrupted / dose increased / dose reduced)

Controlled Quality Management Document		
	Sponsor:	Veru Inc.
	Protocol Number:	V3011902
STATISTICAL ANALYSIS PLAN. PHASE 2-3-4		

- TEAEs leading to treatment discontinuation (drug withdrawn)
- Fatal TEAEs
- For the above AE categories tables including incidence and number of events will be presented by system organ class and preferred term
- TEAEs by system organ class, preferred term and maximum toxicity grade (incidence, no event counts)
- TEAEs by system organ class, preferred term and strongest relationship grade (incidence, no event counts)
- Listing of Deaths (presented in the Table section of the appendices)
- Listing of Serious TEAEs (presented in the Table section of the appendices).

In counting the event number of AEs reported, a continuous event (i.e. reported more than once and which did not cease), will be counted only once; non-continuous AE reported several times by the same subject will be counted as multiple events.

All AEs will be listed.

6.14.2 Laboratory Data

Laboratory data will be collected in local labs and the units need to be made consistent before presenting in summary tables.

Even when same units are used in different labs the normal ranges can vary within each lab parameter. Also in these cases normalization of the data need to be performed.

Laboratory data shift tables (low/normal/high) will be done based on the original ranges used in the local laboratories.

For descriptive statistics, local laboratory results are normalized using location-scale normalization or scale normalization formulas given by Karvanen (2003).

Result Normalization

Location-scale normalization is used when both central lab and local lab have both lower and upper limits for normal specified in the data:

Controlled Quality Management Document			
	Sponsor:	Veru Inc.	
	Protocol Number:	V3011902	
STATISTICAL ANALYSIS PLAN. PHASE 2-3-4			

$$s_{\text{location-scale}} = L_S + (x - L_X) \frac{(U_S - L_S)}{(U_X - L_X)}$$

If location-scale normalization reaches negative value for a parameter then for that parameter scale normalized value will be used instead (giving priority for value using upper normal limit). Scale normalization is used when either central lab or local lab have and only lower or upper limits for normal specified in the data (or location-scale normalization reaches negative value):

$$s_{\text{scale(upper)}} = x \frac{U_S}{U_X} \quad \text{or} \quad s_{\text{scale(lower)}} = x \frac{L_S}{L_X}$$

The notation in the above formulas are as follows:

- s normalized result
- x local laboratory result
- L_X lower normal limit in local lab
- U_X upper normal limit in local lab
- L_S lower normal limit in central lab
- U_S upper normal limit in central lab.

As this study does not have central laboratory then the most common range will be used instead of central lab values in the formula above. This keeps the number of normalized values as low as possible.

Descriptive statistics of the observed values and change from baseline (continuous data) will be presented by treatment group and visit for each chemistry, hematology and urinalysis parameter.

Each measurement (continuous data) will be classed as below, within, or above normal range, based on ranges supplied by the laboratory used. Shift tables in relation to the normal range from baseline to each timepoint will be presented.

A listing of any clinically significant laboratory measurements recorded throughout the study will be presented in tables section.

All laboratory data will be listed. Listings will show the normalized values.

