Treatments:	
Subjects in the VERU-111 treatment groups will receive standard of care, plus oral daily VERU-111 9 mg for 21 days or until released from hospital, whichever comes first.
 
Subjects in the Placebo treatment group will receive standard of care, plus a placebo capsule for 21 days or until released from hospital, whichever comes first.

Procedures:	
Potential study participants will undergo a series of screening evaluations, including the collection of demographic information, within 3 days prior to randomization. Subjects who give written informed consent and satisfy the selection criteria will be enrolled into the study.
 
SpO2 levels will be taken at screening, baseline (Day 1) and on Days 3, 9, 15, 22, and 29.

Veru Inc  
Protocol V3011902 – FINAL Version 7.0

---

	Safety evaluations including assessment of adverse events (Days 1-22, Day 29, Day 45, and Day 60), 12-lead electrocardiogram (single) (screening, Day 15, Day 22, and Day 29) and clinical laboratory results: urinalysis (screening, baseline, Day 22, and Day 29), hematology (screening, baseline, Day 3, Day 9, Day 15, Day 22, and Day 29), and serum chemistry (screening, baseline, Day 3, Day 9, Day 15, Day 22 and Day 29).
--	--

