### **8.9 Subject Stopping Rules**

If, in the opinion of the investigator, the participation in the study is or is becoming detrimental to the well-being of a particular subject, this issue should be discussed with the Medical Monitor for this study and dosing may be discontinued.

In subjects that experience an adverse event of Grade 4 or greater severity according to the Common Terminology Criteria for Adverse Events (CTCAE) version 5 ([https://evs.nci.nih.gov/ftp1/CTCAE/CTCAE\\_5.0\\_2010-06-14\\_QuickReference\\_5x7.pdf](https://evs.nci.nih.gov/ftp1/CTCAE/CTCAE_5.0_2010-06-14_QuickReference_5x7.pdf)) that is deemed to be possible, probably or definitely related to study drug dosing with study drug will be discontinued. Prior to discontinuation of study drug, the grading of the event and causal relationship should be discussed with the Medical Monitor for the study.

Subjects will be discontinued from dosing if AST or ALT levels are  $>5$  times the upper limit of normal, or if AST or ALT levels are  $>3$  times the upper limit of normal along with a total bilirubin elevation of  $>2$  times the upper limit of normal.

Subjects will be discontinued from dosing if Grade 3 diarrhea is observed.

Subjects will be discontinued from dosing if Grade 3 neutropenia is observed.

NOTE: These subject stopping rules are related to the discontinuation of study drug, not discontinuation from the study. Subjects should be followed for efficacy and safety even if study drug is stopped based on these stopping rules.

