6.2.10 Discharge, Early Termination and Unscheduled Visits

Only scheduled post-baseline values will be tabulated. Discharge, early termination and unscheduled visits will be mapped to the closest scheduled post-baseline time point. If subject then having more than one record mapped for specific visit then the closest value to the scheduled time point will be used in the analysis.

All collected data will be presented in subject data listings.

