14.3.1.2.4	Treatment-Related Serious TEAEs by System Organ Class and Preferred Term Safety Set	IP	14.3.1.2.1

Controlled Quality Management Document			
	Sponsor:	Veru Inc.	
	Protocol Number:	V3011902	
STATISTICAL ANALYSIS PLAN. PHASE 2-3-4			

Table Number	Table Title	Validation Method	Shell Number (if repeat)
14.3.1.2.5	TEAEs Leading to Treatment Modification (drug interrupted / dose increased / dose reduced) by System Organ Class and Preferred Term Safety Set	IP	14.3.1.2.1
14.3.1.2.6	TEAEs Leading to Treatment Discontinuation (drug withdrawn) by System Organ Class and Preferred Term Safety Set	IP	14.3.1.2.1
14.3.1.2.7	Fatal TEAEs by System Organ Class and Preferred Term Safety Set	IP	14.3.1.2.1
14.3.1.3.1	TEAEs by System Organ Class, Preferred Term and Maximum Toxicity Grade Safety Set	IP	
14.3.1.3.2	TEAEs by System Organ Class, Preferred Term and Strongest Relationship to Study Treatment Safety Set	IP	
14.3.2.1	Listing of Deaths Safety Set	IP	
14.3.2.2	Listing of Serious TEAEs Safety Set	IP	14.3.2.1
14.3.4.1	Listing of Abnormal Laboratory Values Safety Set	IP	
14.3.5.1.1	Hematology Descriptive Statistics Safety Set	IP	14.2.7.1
14.3.5.1.2	Hematology Shift Table Safety Set	IP	
14.3.5.2.1	Chemistry Descriptive Statistics Safety Set	IP	14.2.7.1
14.3.5.2.2	Chemistry Shift Table Safety Set	IP	14.3.5.1.2

Controlled Quality Management Document		
	Sponsor:	Veru Inc.
	Protocol Number:	V3011902

Table Number	Table Title	Validation Method	Shell Number (if repeat)
14.3.5.3.1	Urinalysis Descriptive Statistics (Continuous) Safety Set	IP	14.2.7.1
14.3.5.3.2	Urinalysis Descriptive Statistics (Categorical) Safety Set	IP	14.2.1.1
14.3.5.3.3	Urinalysis Shift Table Safety Set	IP	14.3.5.1.2
14.3.6.1.1	Vital Signs Descriptive Statistics Safety Set	IP	14.2.7.1
14.3.7.1.1	Physical Examination Shift Table Safety Set	IP	14.3.5.1.2
14.3.8.1.1	ECG Descriptive Statistics Safety Set	IP	14.2.7.1
14.3.8.1.2	ECG Shift Table Safety Set	IP	14.3.5.1.2
14.3.9.1.1	Chest X-Ray / CT Shift Table Safety Set	IP	14.3.5.1.2
14.4.1.1	Descriptive Statistics for Pharmacokinetic Concentrations of Veru-111 (ng/mL) Safety Set	IP	

Controlled Quality Management Document		
	Sponsor:	Veru Inc.
	Protocol Number:	V3011902

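### Grade 3 neutropenia is a mandatory dose stop, but the SAP's laboratory outputs cannot give a reliable per-arm count of subjects who reached it; AE tables cover most, not all, of the gap

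*SAP*

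**What the plan says.** Protocol 8.9 is unconditional: "Subjects will be discontinued from dosing if Grade 3 neutropenia is observed". Neutrophils come from the white cell differential in Protocol Appendix A, and the sampling schedule in Protocol 2.0 is "hematology (screening, baseline, Day 3, Day 9, Day 15, Day 22, and Day 29", so there are five scheduled post-baseline samples.

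The SAP table list (11.1) has two hematology tables: descriptive statistics (14.3.5.1.1) and a shift table (14.3.5.1.2). On the shift table, SAP 6.14.2 says "Laboratory data shift tables (low/normal/high) will be done based on the original ranges used in the local laboratories" and "Shift tables in relation to the normal range from baseline to each timepoint will be presented". For descriptive statistics the same section normalises local results to the most common reference range, and it says that listings show the normalised values.

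SAP 6.2.10 maps discharge, early-termination and unscheduled records to the nearest scheduled visit. Where several records compete, "the closest value to the scheduled time point will be used in the analysis". The same section adds "All collected data will be presented in subject data listings".

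Two further outputs bear on the question. SAP 6.14.2 promises "A listing of any clinically significant laboratory measurements recorded throughout the study will be presented in tables section"; list 11.1 calls output 14.3.4.1 "Listing of Abnormal Laboratory Values Safety Set". SAP 6.14.1 plans treatment-emergent adverse events by preferred term and maximum toxicity grade (14.3.1.3.1) and those leading to drug withdrawal (14.3.1.2.6).

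**The concern.** When a protocol names a toxicity as a reason to stop drug, the reader of the safety section will want to know how many treated subjects in each arm reached it. The count should come from the measurements that trigger the stop. Here the planned laboratory tables carry no grade and no neutrophil cut-off, so the number has to be taken from adverse-event reporting or assembled by hand from a listing.

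The plan uses a more suitable format elsewhere. Protocol 9.7 specifies threshold counts and a baseline-to-maximum category shift for ALT and AST, which are also stopping criteria in 8.9. SAP 6.14.4 and 6.14.5 use baseline-to-worst shifts for physical examination and ECG. Neutrophils have neither. At stake is the safety, tolerability and risk/benefit objective; the mortality analysis is not involved.

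**Working it through.** There is no figure in the plan to reproduce. The check sets the stopping rule against each planned output.

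**1. Shift table: no grade.** Each value is classed as below, within or above the local range. A count at the stopping grade and a count just under the limit fall in the same cell. Using the original local ranges is sound; the classes are too coarse for this purpose.

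**2. Shift table: visits, not subjects.** One subject can be low at several visits. If c subjects are low at each of k visits, the number of different subjects ever low lies between c (the same people each time) and k × c (all different).

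- Dosing ends by Day 21 or at discharge (Protocol 5.2), so the scheduled samples nominally on drug are Days 3, 9 and 15: k = 3. Day 22 has a window of ±3 days, and Day 29 is off drug.
- Assume c = 2. The range is 2 to 3 × 2 = 6 subjects.
- VERU-111, planned n = 140: 2/140 = 1.4% to 6/140 = 4.3%.
- Placebo, planned n = 70: 2/70 = 2.9% to 6/70 = 8.6%.
- With all five visits the range is 2 to 5 × 2 = 10 subjects: 1.4% to 7.1% of 140, or 2.9% to 14.3% of 70.

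By step 1, the table does not show how many of these were Grade 3 or worse.

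**3. Visit rule: nearest in time, not worst.** Suppose a low count is found at an unscheduled Day 13 sample. It is 15 − 13 = 2 days from Day 15 and 13 − 9 = 4 days from Day 9, so it maps to Day 15. If the Day 15 sample was drawn (distance 0), that record is tabulated and the Day 13 nadir is not.

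**4. Descriptive statistics and listings: normalised values.** SAP 6.14.2 gives s = L_S + (x − L_X)(U_S − L_S)/(U_X − L_X). Assume a cut-off of 1.0 ×10⁹/L and the ranges below; none of these is in the documents.

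- Local 1.5–7.5, reference 1.8–7.5, x = 0.9: s = 1.8 − 0.6 × (5.7/6.0) = 1.23. A value under the cut-off moves above it.
- Local 1.8–7.5, reference 1.5–7.5, x = 1.2: s = 1.5 − 0.6 × (6.0/5.7) = 0.87. A value above the cut-off moves under it.
- With matching ranges nothing changes. With the SAP's upper-limit scaling fallback the factor is 7.5/7.5 = 1, so both values are unchanged. In the second mapping the fallback applies only when s would be negative, that is for x < 1.8 − 1.5 × (5.7/6.0) = 0.375.

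The by-visit minimum therefore cannot be used even to tell no cases from at least one. It is a normalised value, and it can miss a record displaced under step 3.

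**5. Listing 14.3.4.1.** It covers the whole study, and SAP 6.3 sorts listings by treatment group, so a hand count is possible. Its entry criterion is clinical significance in 6.14.2 and abnormality in 11.1. Neither is a grade, and the values shown are normalised.

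**6. Adverse-event tables.** These do count subjects by arm. Their limits are:

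- Protocol 8.11 ties laboratory abnormalities to symptoms, treatment or worsening of a pre-existing condition. An asymptomatic, untreated low count may therefore go unreported.
- A Grade 3 count first found after the last dose triggers no drug withdrawal and so cannot enter 14.3.1.2.6.
- A missing grade is set to Grade 3, which the SAP expects to be rare.

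**The case against.** The strongest reply is that the number is already available outside the laboratory tables. Table 14.3.1.3.1 is a per-subject count of the worst grade by preferred term, by treatment received. Steps 1 to 4 do not touch it. A subject who meets the 8.9 rule has drug stopped and a reason recorded (Protocol 8.10), and SAP 6.4 summarises withdrawal reasons by arm. The adverse-event definition in 8.11 can be read broadly, and the grading scale in 8.11.1 provides for asymptomatic findings. This stands for most cases that stop drug. It does not cover a count that the site never records as an adverse event.

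It is also true that Protocol 9.7 asks for category counts only for ALT and AST, that SAP section 6 allows further tables in the study report, that all collected data are listed, and that the IDMC sees unblinded safety data about every four weeks. With about 210 subjects a hand count is feasible. These facts limit the severity. They do not make the listing a safe source where local ranges differ, because the SAP does not commit to showing original values beside the normalised ones.

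A reader might infer that Grade 3 neutropenia goes uncounted altogether, or that the SAP assigns toxicity grades from normalised values. The documents support neither: the adverse-event tables count graded events, and no output grades laboratory values at all.

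**Conclusion.** The point holds as a minor gap in safety reporting. No planned laboratory output gives a reliable number of subjects per arm who reached the neutropenia stopping grade. The remaining gap after the adverse-event tables is Grade 3 or worse counts not reported as adverse events.

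Its size cannot be estimated: the documents give no neutropenia rate and no local reference ranges. The 2-to-6 range (2 to 10 over all five visits) shows only what a by-visit table leaves open and rests on an assumed 2 low subjects per visit and the planned arm sizes. The normalisation examples rest on an assumed cut-off and assumed ranges, and vanish where ranges match.

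It would be wrong to conclude that a protocol commitment is broken or that the primary analysis is affected.

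**What to change.** (a) SAP 6.14.2 and list 11.1: add one Safety Set table of baseline CTCAE v5 neutrophil grade by worst post-baseline grade, by treatment received, with n (%) of subjects with new Grade 3 or worse. Use all post-dose records (scheduled, unscheduled, discharge and early termination) and unit-harmonised, un-normalised values. Where neutrophils are reported as a percentage, derive the absolute count from the white cell count and differential, both in Appendix A.

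(b) SAP 6.2.10: state that this worst-grade laboratory table is exempt from the one-record-per-visit rule. The exemption need not extend to other tables.

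(c) SAP 6.14.2: replace the listing sentence with: *Listings will show the original and the normalized values.*

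The cost is one table and two short edits, with data already collected and no new visits or samples. The table may show more laboratory toxicity than the adverse-event tables, and the report would have to explain the difference. It cannot recover episodes that were never sampled.

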### **9.7 Safety Analysis**

The frequency of adverse events (AEs) will be tabulated by MedDRA term and system organ class. The incidence of AEs and the maximum intensity and frequency of AEs will be

summarized. A new onset AE is defined as an AE that was not present prior to treatment with study medication but appeared following treatment or was present at treatment initiation but worsened during treatment. An AE that was present at treatment initiation but resolved and then reappeared while the subject was on treatment is a new-onset AE (regardless of the intensity of the AE when the treatment was initiated).

All laboratory results, vital sign measurements, and other safety variables will be summarized using appropriate descriptive statistics. Changes from baseline will be computed and will be summarized using appropriate descriptive statistics.

A summary of the number of subjects developing treatment emergent values of ALT and AST  $\geq 3x$  ULN,  $5x$  ULN, and  $10x$  ULN, respectively and a shift table for individual subjects shifts from baseline to maximum observed value by category:  $<3x$  ULN,  $\geq 3x$  ULN,  $\geq 5x$  ULN and  $\geq 10x$  ULN will be provided. Additionally, a summary of patients that develop Drug Induced Liver Injury by Hy's Law will be provided.

Safety data will be summarized utilizing the SAF analysis set.

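### The SAP omits the protocol's ALT/AST multiple-of-ULN and Hy's law outputs, and its normalized laboratory listings need not preserve those multiples

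*SAP*

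**What the plan says.** Protocol 9.7 (Safety Analysis) sets out three liver outputs:

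- "A summary of the number of subjects developing treatment emergent values of ALT and AST" at 3x, 5x and 10x ULN;
- "a shift table for individual subjects shifts from baseline to maximum observed value by category", with cut points at the same three multiples;
- "a summary of patients that develop Drug Induced Liver Injury by Hy's Law will be provided".

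SAP 6.14.2 (Laboratory Data) plans descriptive statistics by visit, low/normal/high shift tables from baseline to each timepoint on the local laboratories' own ranges, and a listing of clinically significant values. For the descriptive statistics, "local laboratory results are normalized using location-scale normalization or scale normalization formulas". The target range is a substitute: "As this study does not have central laboratory then the most common range will be used instead of central lab values in the formula above". The section ends by saying that all laboratory data are listed and that "Listings will show the normalized values".

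SAP 11.1 has chemistry descriptive statistics (14.3.5.2.1), one chemistry shift table (14.3.5.2.2) and a listing of abnormal laboratory values (14.3.4.1). The legible part of SAP section 9 names three changes from the protocol: the randomization strata, the WHO score analysis and the Holm procedure.

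**The concern.** The protocol treats the liver as a named safety issue. Several exclusion criteria in 6.2.2 are hepatic, and protocol 8.9 ties discontinuation of dosing to multiples of ULN for AST/ALT, alone or together with bilirubin. A reader of the final outputs will want to know who crossed those multiples, by arm.

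The SAP's outputs do not answer that question. A low/normal/high table puts 1.1x and 10x ULN in the same cell, and no planned table joins ALT/AST with bilirubin. If a reader turns to the listings to fill the gap, the values there have been transformed, and the transformation need not preserve the multiple of ULN on which the protocol's categories are built.

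**Working it through.** **Step 1. Protocol outputs against SAP outputs.**

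| Protocol 9.7 | Nearest item in SAP 6.14.2 / 11.1 | What is missing |
|---|---|---|
| Counts at 3x, 5x, 10x ULN | Low/normal/high classification | Size of the elevation |
| Shift from baseline to maximum, by multiple | Shift from baseline to each timepoint, by normal range | The maximum and the multiples |
| Hy's law summary | None | Joint ALT/AST and bilirubin pattern |

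SAP 6.2.10 widens the second gap. Unscheduled results are mapped to the closest scheduled visit, and where several results compete for a visit, the one nearest the scheduled time is used. A peak from an unscheduled draw can therefore drop out of the tables. A baseline-to-maximum table would catch it. The SAP already uses worst post-baseline shifts for physical examination (6.14.4) and ECG (6.14.5).

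**Step 2. What normalization does to a multiple of ULN.** The location-scale formula in SAP 6.14.2 is s = L_S + (x − L_X)(U_S − L_S)/(U_X − L_X), with X the local and S the reference range. Write m = x/U_X for the true multiple of local ULN, a = L_X/U_X and b = L_S/U_S. Dividing by U_S gives

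s/U_S = b + (m − a)(1 − b)/(1 − a).

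- At m = 1 this is b + (1 − b) = 1 for any a and b, so status above or not above ULN is never changed.
- For m > 1 it equals m only if a = b.
- Upper-limit scaling, s = x·U_S/U_X, gives s/U_S = m exactly.

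**Step 3. Size.** The documents give no laboratory ranges. As an assumption, let the local ratio a run from 0 to 0.25. The SAP uses one reference range, so b is held fixed in each row. Examples for m = 3:

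- b = 0, a = 0.25: (3 − 0.25)/0.75 = 3.67.
- b = 0.125, a = 0: 0.125 + 3 × 0.875 = 2.75.
- b = 0.125, a = 0.25: 0.125 + 2.75 × 0.875/0.75 = 3.33.
- b = 0.25, a = 0: 0.25 + 3 × 0.75 = 2.50.

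Listed multiple over a = 0 to 0.25, by the same formula:

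| Reference ratio b | True 2x (bilirubin) | True 3x | True 5x | True 10x |
|---|---|---|---|---|
| 0 | 2.00-2.33 | 3.00-3.67 | 5.00-6.33 | 10.00-13.00 |
| 0.125 | 1.88-2.17 | 2.75-3.33 | 4.50-5.67 | 8.88-11.50 |
| 0.25 | 1.75-2.00 | 2.50-3.00 | 4.00-5.00 | 7.75-10.00 |

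Without the original result or the local range, a reader cannot work back from s to m.

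**The case against.** Several stronger readings are tempting, and the documents do not support them.

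- **That the listings show only normalized values.** The SAP does not say so; it is silent on original results. SAP 6.2.10 says "All collected data will be presented in subject data listings", but that sentence closes a section on visit mapping, so it is weak evidence of a contradiction. The layout is unclear, and that is as far as the text goes.
- **That liver injury would be invisible.** Values above ULN appear in shift tables on local ranges, in the clinically significant and abnormal-value listings, and in part in the adverse event tables. The adverse event route is incomplete, because protocol 8.11 counts a laboratory abnormality only if it comes with symptoms or needs treatment. The descriptive statistics include a maximum by visit, so a very high value would show approximately, though not linked to bilirubin.
- **That one trial could list a true 3x anywhere from 2.50x to 3.67x.** With a single reference range for a parameter, the low and high ends belong to different reference ratios and cannot occur together.
- **That distortion is certain.** It is zero when the ratios match, when the local range is the reference range, and when upper-limit scaling applies. The SAP switches to upper-limit scaling if location-scale gives a negative value for a parameter. If that is applied to the whole parameter, one such value removes the problem.

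It is also fair to say that text near SAP section 9 is redacted, that the IDMC plan is a separate document not available here, and that SAP section 6 allows additional tables in the study report. The first does not affect the table list, which shows the omission independently. The last is a permission, not a commitment.

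What stands is the narrowing of the listing issue. The missing outputs are not answered by any of this.

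**Conclusion.** The point holds in two parts of unequal strength. The first is documentary and needs no assumption: three outputs that protocol 9.7 commits to are absent from SAP 6.14.2 and 11.1, with no explanation in the legible text. What is lost is the size of ALT/AST elevations and their joint pattern with bilirubin; above-ULN status is kept.

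The second part is conditional. If listings carry the normalized value without the original result and local range, multiples of ULN can be misstated in either direction. Under the assumed local ratios of 0 to 0.25, a true 3x moves by at most 0.67 upward (reference ratio 0) or 0.50 downward (reference ratio 0.25). Whether any material shift would occur is unknown, because the ranges are not given.

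**What to change.** 1. Add to SAP 6.14.2 and 11.1 the three outputs of protocol 9.7: ALT/AST counts at 3x, 5x and 10x ULN, the shift from baseline to maximum by those categories, and the Hy's law summary. Compute each multiple as original result divided by local ULN, which is exact for any range, and use all post-baseline values, including unscheduled ones. If the sponsor means to drop any of these outputs, SAP section 9 should say so and give the reason.
2. In the laboratory listings (16.2.8.1 to 16.2.8.3) and Table 14.3.4.1, show the original result, the local range and the multiple of local ULN beside the normalized value, where a numeric range exists.

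The cost is a few tables and listing columns from data already collected. Nothing changes in trial conduct or in the efficacy analyses.
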